### **11.1.3 Preoperative Variables Collected**

Following finalization of informed consent the patient's chart will be reviewed to ensure that they are appropriate for participation based upon the study's inclusion and exclusion criteria.

Additionally, the patient's records will be reviewed and key demographics and clinical variables will be collected using a standardized data collection tool. 11.1.3.1 Demographics and clinical variables collected

Age	+/- Recent MI
Gender	+/- CHF
Race	+/- DM Type II (insulin)
Height	+/- DM Type II (non-insulin)
Weight	+/- Renal Insufficiency
BMI	+/- COPD
Serum creatinine	+/- OSA
Hemoglobin	+/- Dementia
LVEF	+/- Alcohol use
+/- Vascular disease	+/- Tobacco use
+/- Stroke/TIA	+/- Illicit drug use
+/- CAD	

## 11.2 Protocol Assessments and Procedures – Baseline Acquisition Period

### 11.2.1 General Baseline Acquisition Period Description

During the baseline acquisition period each subject will be randomized and then the neurocognitive baseline exams will be obtained. Additionally, the baseline rSO2 data will be collected.

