## 7.2 Study Periods

### 7.2.1 Screening Period

Assessing patient's suitability for enrollment based upon defined inclusion and exclusion criteria. The informed consent process and enrollment will occur during this period after which preoperative demographics and study defined covariates will be recorded.

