### 7.2.2 Baseline Acquisition Period

Following randomization using an envelope randomization technique to either the control or intervention cohort enrolled subjects will undergo baseline testing with the MMSE and CAM assessment tools. Subsequently all subjects will have acquisition of bifrontal NIRS cerebral oximetric readings on both room air and with 100% oxygen supplementation. The control group and the intervention group will have open NIRS baseline data collection. This will allow all enrolled subjects to demonstrate that a set of baseline rSO2 values can be obtained and thus reduce the probability of unreadable outliers (i.e. subjects with anomalously located frontal sinuses) being studied in the control group. The baseline acquisition will occur in the operating room just prior to anesthesia induction.

[figure not shown]

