### 9.1.1 Inclusion Criteria:

1. Any male or female patient  $\geq 65$  years of age and able to provide informed consent (or consent may be provided by a legally authorized representative) who is scheduled for a thoracic surgical procedure that is expected to involve the use of intraoperative single lung ventilation (SLV)
2. Able to adequately complete a baseline mini-mental status examination (MMSE)

3. Able to complete a baseline confusion assessment method (CAM) examination
4. Able to obtain bi-frontal baseline rSO2 values prior to induction of anesthesia

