### 11.2.2 Randomization

Next, each subject will be randomized in a balanced fashion (1:1) to either the control group or the intervention group. Randomization will occur through the use of a blinded envelope technique at which time each subject will acquire a unique study identifier for their study records.

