### 11.2.3 MMSE and CAM Baseline Exams Performed

The mini-mental status examination and the confusion assessment method examination will be performed upon each subject to establish baseline performance prior to entering the operating room for their surgical procedure. A trained study investigator will conduct these two exams.

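### Subjects are randomised before inclusion criteria 2 to 4 are tested, and no analysis set says whether those who then fail or lose NIRS signal stay in the clinical comparison

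*Combined protocol and SAP*

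**What the plan says.** **Order.** Section 7.2.2 reads: "Following randomization using an envelope randomization technique to either the control or intervention cohort enrolled subjects will undergo baseline testing". Section 11.2.1 agrees: "During the baseline acquisition period each subject will be randomized and then the neurocognitive baseline exams will be obtained". Sections 11.2.2 to 11.2.4 keep that sequence: allocation, then MMSE and CAM before the operating room, then the two rSO2 baselines inside it. Table 1 lists eligibility review under Screening only. It puts randomisation, the baseline MMSE and CAM, and the baseline rSO2 together under Baseline Acquisition.

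**Eligibility.** In Section 9.1.1, criteria 2 and 3 require a completed baseline MMSE and CAM. Criterion 4 begins "Able to obtain bi-frontal baseline" and refers to rSO2 readings before induction. Section 7.2.1 has screening assess "suitability for enrollment based upon defined inclusion and exclusion criteria", Section 11.1.1 describes an approach in the preoperative area, and Section 11.1.3 describes a chart review after consent. None of these is said to carry out the MMSE, the CAM or a sensor reading.

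**Baseline conditions.** Section 7.2.2: "The control group and the intervention group will have open NIRS baseline data collection". Section 10.2 expects that some people will not give a valid reading. On the MMSE and CAM, Section 11.2.3 says "A trained study investigator will conduct these two exams" and does not say whether that person knows the arm.

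**Withdrawal and analysis.** Section 9.2 has the principal investigator withdraw a subject whose oximetry is lost for long enough to prevent useful analysis; the duration is not defined. Section 15 names tests but no analysis set, no as-allocated rule and no rule for missing data.

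**Target.** The Synopsis and Section 7.1 randomise 100. Section 9.1 enrols 100 evaluable subjects and does not define evaluable.

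**The concern.** Section 6.2 asks which outcomes diverge because of the randomised assignment. That question is answered by comparing everyone allocated to one arm with everyone allocated to the other. A subject who fails a baseline reading or loses NIRS signal still has a hospital stay, a readmission status and most components of the composite. As written, the plan lets such subjects leave the comparison after allocation.

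Two things are at stake. Precision is lost from a 100-subject pilot. And if removal differs by arm and is related to outcome, the choice of endpoints for the larger trial could be biased. Later signal loss is where a difference between arms is most plausible. The intervention display is open and watched by clinicians and a research assistant (Section 10.3), while control values are hidden (Section 10.2). This is an inference; the documents do not say that loss will differ.

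**Working it through.** The plan gives no power, effect size, event rate or loss rate, so there is no stated figure to reproduce. From the documents: 100 subjects, 1:1, hence 50 per arm (Section 7.1), and a 0.05 threshold, which Section 15 attaches to the logistic regression. Two-sided testing, a 50% composite rate and every loss rate below are assumptions. The composite is treated as a difference in proportions with a normal approximation.

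**A. Baseline failure, equal in both arms.** With loss w, n per arm = 50(1 − w) and SE = √(2 × 0.25 / n).

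| w | n per arm | SE (points) | 95% half-width (points) | Wider by |
|---|---|---|---|---|
| 0 | 50 | 10.0 | 19.6 | – |
| 5% | 47.5 | 10.3 | 20.1 | 2.6% |
| 10% | 45 | 10.5 | 20.7 | 5.4% |
| 20% | 40 | 11.2 | 21.9 | 11.8% |

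Both arms have the same open baseline, so equal failure brings no systematic bias. For a continuous outcome, the difference detectable with 80% power is (1.960 + 0.842)√(2/n). It rises from 0.56 SD at n = 50 to 0.59 SD at n = 45 and 0.63 SD at n = 40. If allocation followed the baselines, this loss would be zero. To randomise 100 would then take 100/0.95 = 105.3 → 106, 100/0.90 = 111.1 → 112, or 100/0.80 = 125 consented subjects.

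**B. Later signal loss, unequal between arms, no true effect.** With event rate q among those removed, the retained rate is (0.50 − wq)/(1 − w). The other arm loses 5%.

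- At q = 0.75 the 5% arm keeps (0.50 − 0.0375)/0.95 = 48.68%.
- Losses of 10%, 15% and 20% in the first arm leave 47.22%, 45.59% and 43.75%.
- The spurious differences are 1.5, 3.1 and 4.9 points.
- With SEs of 10.4, 10.5 and 10.7 points, the nominal 5% error becomes 5.2%, 6.0% and 7.5%.

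For q from 0.60 to 0.90 the range is 0.6 to 7.9 points, and 5.0% to about 11.5% error. If q = 0.50, or if both arms lose the same share with the same q, the bias is zero.

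With a 30% event rate instead, losing 20% against 5% gives 3.0 points if those removed have 1.5 times the average risk, and 5.9 points at twice the risk. The direction reverses if the other arm loses more.

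**C. Target.** With 10% or 20% loss after allocation, 100 randomised leaves 90 or 80 evaluable, while 100 evaluable needs 112 or 125 randomised. The two statements of the target therefore differ by 12 or 25 subjects.

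**The case against.** The best defence starts from Section 7.4.1, which defines the primary endpoints as relationships between the oximetry data and clinical variables. A subject without usable rSO2 cannot contribute to those, so withdrawal is consistent with that definition. The Synopsis also says enrolled subjects are followed through the hospitalisation and to 30 days, and Section 15 moves all case report form data into the database. Discarding outcomes is thus not announced, and the gap is a silence. Part A is small on its own figures. If the evaluable target in Section 9.1 allows replacement, the precision loss becomes extra recruitment. Part B rests wholly on assumed rates. With dozens of outcomes tested without multiplicity control, a shift from 5% to 7.5% on one test counts for little.

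Much of this is fair as to size. Criterion 4 alone needs the operating room; the MMSE and CAM could be done before allocation even under the present logistics. That the arm may be known at the baseline exams is likewise an inference from silence.

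The core remains. Section 7.4.1 justifies leaving a subject out of analyses that use rSO2, but not out of the comparison between arms in Section 6.2. Follow-up and data transfer are not an as-allocated rule. Replacing subjects after allocation restores numbers, not the randomised comparison.

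**Conclusion.** The concern holds. The order of allocation is consistent across Sections 7.2.2 and 11.2 and Table 1, and it conflicts with inclusion criteria 2 to 4 and with the statement in Section 7.1 that eligible subjects are randomised. No section says whether subjects who fail a baseline or are withdrawn for signal loss stay in the clinical comparison.

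The missing analysis set matters most. Baseline failure mainly costs subjects and precision, and biases the comparison only if knowledge of the arm affects the judgement. Later signal loss can bias the comparison, but only if removal is unequal between arms and related to outcome. The size of any bias is unknown, and it is modest in most of the assumed cases. This should be fixed because it is avoidable at low cost; it does not invalidate the trial.

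**What to change.** 1. **Order.** In Sections 7.2.2, 11.2.1 and 11.2.2 and Table 1, open the envelope only after the MMSE, CAM and both rSO2 baselines are recorded and before control blinding is activated (Section 11.2.4.3). In Table 1, move the randomisation row below the baseline rSO2 row and add eligibility review to the Baseline Acquisition column. Count subjects who fail criteria 2 to 4 as screen failures, with no envelope used.
2. **Analysis set.** In Sections 9.2 and 15, state: *All randomised subjects are analysed as allocated for every clinical outcome, using available data. Loss of NIRS signal removes a subject only from analyses that use the rSO2 data. Losses are reported by arm with reasons.* If item 1 is not feasible, this wording alone still protects the clinical comparison. Section 15 would then also need a rule for change scores that lack a baseline MMSE.
3. **Target.** Align Section 9.1 with the Synopsis and Section 7.1 as 100 randomised, which avoids replacing subjects after allocation.

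Exclusion criterion 2 and medical discontinuation under Section 9.2 stay as they are.

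**Cost.** Items 2 and 3 are wording only, and some randomised subjects will lack rSO2 AUC data. Item 1 moves allocation into the operating room, between the oxygen-supplemented baseline and induction. The envelope, a blinding-capable device (Section 8.6) and the PICIS set-up (Section 11.3.2) must be ready at each case; the documents do not say how many modified devices are available. A temporary screening number is needed, because randomisation is the point "at which time each subject will acquire a unique study identifier for their study records".

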### 11.2.2 Randomization

Next, each subject will be randomized in a balanced fashion (1:1) to either the control group or the intervention group. Randomization will occur through the use of a blinded envelope technique at which time each subject will acquire a unique study identifier for their study records.

### 11.2.3 MMSE and CAM Baseline Exams Performed

The mini-mental status examination and the confusion assessment method examination will be performed upon each subject to establish baseline performance prior to entering the operating room for their surgical procedure. A trained study investigator will conduct these two exams.

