$AUC_{SpO_2} < 75\%$  regardless of intraoperative  $FiO_2$  values

$AUC_{SpO_2} < 70\%$  regardless of intraoperative  $FiO_2$  values

- Time from procedure completion to arrival in the post anesthesia care unit (PACU) or ICU
- Temperature upon PACU/ICU arrival
- Aldrete score upon PACU/ICU arrival and at 30 & 60 (or at discharge) min post-PACU arrival (See Appendix A)
- Any occurrence of immediate postoperative atrial fibrillation
- Any myocardial ischemia in the immediate postoperative period
- Any need for allogeneic RBC transfusion in the immediate postoperative period
- Any observed stroke or TIA in the immediate postoperative period
- Time to clinical readiness for PACU discharge as assessed by established institutional discharge criteria (see Appendix B)
- Frequency and severity of nausea and vomiting observed in the PACU and/or ICU as assessed by an accepted postoperative nausea and vomiting scale
- ICU length of stay (ICU-LOS) [anticipated to be at least 10-20 evaluable subjects for this parameter if 100 patients are enrolled] which will be defined as time to clinical readiness for ICU discharge as assessed by the clinical team caring for the patient
- Postoperative mechanical ventilation time if still intubated and admitted to the ICU following the surgical procedure
- Use of any immediate postoperative, intravenous vasopressor and/or inotropic agent (as assessed by amount of time in minutes on any IV drug support regardless of dose and assessed by total dose of drug delivered to patient)
- Immediate postoperative urine output in any patient with an indwelling foley catheter as assessed by mLs urine/kg/hr for total time in operating room
- Hospital length of stay (H-LOS)
- Need for skilled nursing facility/rehabilitation hospital admission upon discharge from index hospitalization
- Length of time spent in a skilled nursing facility/rehabilitation hospital upon discharge from index hospitalization if a relevant data point for each subject

- Need for hospital readmission for any reason within 30 days of surgical procedure
  - Observed change from preoperative baseline Mini-mental Status Examination (MMSE) score (including postoperative day #1 and postoperative day #3 or discharge scores)
  - Presence/absence of postoperative delirium (as assessed by the CAM Delirium assessment tool results obtained preoperatively and postoperatively upon PACU discharge, Day#1 and 3 [or hospital discharge])

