### **10.3 Intervention Group**

The intervention group will have baseline NIRS values obtained in a manner analogous to the control group. Following recording of the baseline values the subjects will be induced into general anesthesia and the clinicians as well as an IRB registered research assistant will be able to openly monitor the NIRS data. Upon observed cerebral desaturations greater than 20% of the oxygen supplemented baseline on either frontal hemisphere the research assistant will inform the anesthesia clinician that a significant cerebral desaturation is occurring and requires treatment. At this point a standardized interventional protocol will be followed that is detailed in Appendix C. The clinicians caring for the subject will have the ability to override the study intervention algorithm based upon the patient's physical condition at the time.

The intervention protocol for observed desaturations >20% will involve insuring that the subject's head vessels are not kinked or obstructed, increasing the mean arterial pressure via an intravenous fluid bolus or administration of a vasoconstrictor (i.e. phenylephrine or ephedrine) as deemed appropriate by the anesthesia clinician caring for the subject, normalizing PaCO2 to a value between 40 to 50 mmHg, or alternatively normalizing end tidal CO2 to a value of 35 to 45 mmHg. Subsequent interventions may include increasing the FiO2, especially if the SpO2 is below 98% or administering an intravenous inotropic agent if a low flow state is suspected. Administration of an inotrope will occur as judged by the clinician caring for the subject. Finally, in cases where the subject's hematocrit is known or suspected to critically low transfusion of allogeneic blood will be considered. The decision to transfuse allogeneic blood will be made by the anesthesia and surgery clinicians caring for the subject.

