## **11 PROTOCOL ASSESSMENTS AND PROCEDURES**

The Schedule of Assessments which details the sequence of assessments and procedures is presented in Table 1. Note that as described in Section 7.2 there are four separate periods that this study is divided into that include the following: screening, baseline, intraoperative and immediate postoperative and postoperative follow up.

Table 1: Schedule of Assessments

	Screening	Baseline Acquisition	Intraoperative and Immediate Postoperative	Postoperative Follow Up
Study Assessment				
Review of inclusion/exclusion criteria	X			
Informed consent	X			
Demographics	X			
Medical history	X			
Randomization		X		
MMSE & CAM testing		X		X
Serum creatinine	X			X
Obtain baseline room air and O 2 supplemented rSO 2		X		
Continuous rSO 2 , SpO 2 , blood pressure data collection			X	
Employ rSO 2 desaturation algorithm (intervention group only)			X	
Continuous intra/immediate post-operative clinical variable collection			X	
PACU and ICU clinical variable collection			X	
Postoperative clinical variable collection			X	X
Adverse and Serious Adverse Event Monitoring		X	X	X
Telephone interview				X

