#### 11.4.2 Postoperative Day 1 and 3 MMSE and CAM Assessments

The MMSE and the CAM assessment will be repeated on each subject on postoperative days 1 and 3.

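### Randomisation comes before the baseline MMSE and CAM, and nothing keeps the arm from the examiner at any time point, so the neurocognitive endpoints are open to differential scoring

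*Combined protocol and SAP*

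**What the plan says.** **Order.** Two sections agree. Section 7.2.2: "Following randomization using an envelope randomization technique to either the control or intervention cohort enrolled subjects will undergo baseline testing with the MMSE and CAM". Section 11.2.1: "each subject will be randomized and then the neurocognitive baseline exams will be obtained". Table 1 puts randomisation and the MMSE/CAM in the same column, so it does not contradict them.

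**Examiner.** For the baseline exams, section 11.2.3 says: "A trained study investigator will conduct these two exams". It places them before the subject enters the operating room. For the later exams, section 11.4.2 says only: "The MMSE and the CAM assessment will be repeated on each subject on postoperative days 1 and 3". Section 7.4.1.2 adds a further CAM time point: "CAM Delirium assessment tool results obtained preoperatively and postoperatively upon PACU discharge". No examiner is named for any postoperative exam.

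**Blinding.** The plan uses the term for two things only. One is the control-arm NIRS display (7.1, 7.2.3, 8.6, 10.2, 11.2.4.3). The other is the assignment method in 11.2.2: "Randomization will occur through the use of a blinded envelope technique". In the intervention arm, section 10.3 says: "the clinicians as well as an IRB registered research assistant will be able to openly monitor the NIRS data".

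**Role of the exams.** MMSE change from baseline and presence of delirium are both listed under 7.4.1 Primary Endpoints. Section 9.1.1 also makes adequate completion of the baseline MMSE, completion of the baseline CAM, and obtainable bi-frontal rSO2 values conditions of inclusion.

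**The concern.** The MMSE and CAM are administered by a person, and that person can influence the result. If the examiner knows the arm, small differences in prompting or crediting answers can differ between arms. The MMSE endpoint is a change score, so drift at baseline matters as much as drift after surgery: bias in the change equals postoperative bias minus baseline bias. Since randomisation comes first, the plan does not protect even the baseline half.

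Blinding the control display does not help. It hides the NIRS values, not the allocation, and a console without readings itself identifies a control subject. The CAM at PACU discharge is the most exposed, because section 7.2.3 keeps monitoring running until that point.

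The eligibility judgements are a second exposure. Whether a subject completed the MMSE adequately is a matter of judgement, and the stated order has it made after allocation, so exclusions could differ by arm.

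The stake follows from section 6.2. The pilot exists to pick the outcomes that diverge between arms and carry them into a multicentre trial. A scoring artefact in MMSE or delirium could be picked in this way.

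**Working it through.** The plan states no power, effect size or SD, so there is no figure of its own to reproduce. The finding rests on the text; the arithmetic only shows how much drift would matter.

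**Text check**

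| Time point | Examiner named? | Arm already allocated? | Examiner kept unaware? |
|---|---|---|---|
| Baseline (7.2.2, 11.2.1, 11.2.3) | Yes, a study investigator | Yes | Not stated |
| PACU discharge, CAM (7.4.1.2) | No | Yes | Not stated |
| Days 1 and 3 (7.2.4, 11.4.2) | No | Yes | Not stated |

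**When the arm is first needed.** Both groups have open baseline rSO2 readings (7.1, 7.2.2). The arms first diverge when the control display is blinded, after those readings (11.2.4.3). No baseline procedure requires the arm to be known earlier.

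**MMSE illustration.** Inputs:
- n = 50 per arm (100 subjects, 1:1; Synopsis and 7.1).
- Level 0.05. Section 15 attaches it to the logistic regression and does not give the sidedness; two-sided is assumed.
- No true effect.
- SD of MMSE change of 2, 2.5, 3 or 4 points: assumed.
- Average scoring drift between arms of 0.25, 0.5 or 1 point: assumed.

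For a two-sample t-test the non-centrality is δ = (drift/SD) × √(n/2) = 5 × drift/SD. The chance of p < 0.05 is P(|T| > 1.984), with T non-central t on 98 degrees of freedom. For example, drift 0.5 and SD 2.5 give δ = 5 × 0.2 = 1.0 and a probability of 16.8%.

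| Drift (points) | SD 2 | SD 2.5 | SD 3 | SD 4 |
|---|---|---|---|---|
| 0 | 5% | 5% | 5% | 5% |
| 0.25 | 9.5% | 7.9% | 7.0% | 6.1% |
| 0.5 | 23.6% | 16.8% | 13.1% | 9.5% |
| 1 | 69.7% | 50.8% | 37.9% | 23.6% |

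Section 15 names the Wilcoxon rank-sum test for group differences. Simulating it on scores rounded to whole points gives slightly lower values: for a 1-point drift, about 67%, 49%, 36% and 22%.

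**Binary illustration.** Take the same event rate in both arms, with some events missed in the intervention arm only, and a pooled z test enumerated exactly. At 29% (the rate of decreased MMSE at 3 hours in the observational study cited in the Study Rationale), missing 10%, 20%, 30% or 50% of events gives p < 0.05 in 6.3%, 10.2%, 17.3% or 42.8% of trials. At an assumed 10% rate, the same range of missed events gives 5.3% to 14.5%.

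**The case against.** **The documents do not show unblinded assessment.** This stands. A reader might infer that the baseline is scored with the arm known, or that study investigators do the later exams. Neither is stated. The plan does not say who opens the envelope or who learns the result, and it names no postoperative examiner. What is missing is a safeguard.

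**The illustration depends on its assumptions.** This also stands. A reader might take 70% as the size of the problem. It needs a full point of drift averaged over an arm and an SD of 2, which is half an SD. At 0.25 points the rate stays near the nominal 5%.

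**This is a pilot.** It screens many variables, a later randomised trial is to test what it finds, and neither MMSE nor CAM enters the composite endpoint in 7.4.1.2. That limits the harm. It does not remove it, because choosing endpoints is the pilot's stated purpose.

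**Staffing is not shown.** A reader might infer that the present team can supply an unaware examiner at no cost, since the plan mentions investigators, a nurse coordinator (11.1.1), a research assistant (10.3) and a study team member for calls (11.4.4). The plan gives no staffing numbers and does not say that anyone other than the study investigator is trained for these exams. The research assistant watches the open display, so cannot be the unaware examiner for those subjects. This objection limits the postoperative remedy. It does not touch the change of order.

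**Conclusion.** The concern holds in this form: by the plan's own order the arm is assigned before the baseline MMSE and CAM, and no provision keeps it from the examiner at baseline, at PACU discharge, or on days 1 and 3. Two endpoints listed as primary are open to differential scoring, and the MMSE, CAM and rSO2 eligibility checks follow allocation.

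Neither the direction nor the size of any bias can be derived from the documents. Under the assumed drifts and SDs, the false-positive rate for one MMSE comparison runs from close to 5% to about 70%; half a point of drift gives roughly 9% to 24%. If drift is removed, the rate returns to 5%.

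The change of order is worth making on its own, because it corrects a stated rule at little cost. The unaware postoperative examiner is desirable but depends on staffing that the documents do not describe.

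**What to change.** 1. **Open the envelope later.** Amend 7.2.2, 11.2.1 and 11.2.2 so that it is opened only after the baseline MMSE and CAM are complete. Preferably wait until both sets of baseline rSO2 readings are recorded, so that these three inclusion criteria in 9.1.1 are settled before allocation.
2. **Name the postoperative examiner.** Where existing trained team members allow, use someone who was not in the operating room, PACU or ICU for that subject and is not shown the allocation.
3. **Record awareness.** Add one field to each MMSE/CAM form stating whether the examiner knew the arm.
4. **Reconcile the schedule.** Section 7.4.1.2 lists a CAM at PACU discharge that 7.2.4 and 11.4.2 omit. If it is kept, state who performs it, since the display may still be in use.

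**Cost.** Step 1 needs no extra staff or procedure, but allocation falls later. If it follows the rSO2 readings, it comes close to induction. The study identifier, issued at randomisation under 11.2.2, and the device set-up for either arm must then be ready in advance. Randomising straight after the MMSE and CAM avoids that pressure but leaves the rSO2 eligibility check after allocation. Step 2 costs rota effort, and possibly training. Steps 3 and 4 are edits to forms and text. The sample size does not change.
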